## 9.7. Appendix 7: Values of Potential Clinical Importance

### 9.7.1. Laboratory Values

Haematology				
Laboratory Parameter	Units	Category	Clinical Concern Range	
			Low Flag (< x)	High Flag (>x)
Hematocrit	Ratio of 1			0.54
		Δ from BL	↓ 0.075	
Haemoglobin	g/L			180
		Δ from BL	↓ 25	
Lymphocytes	x10  / L		0.8	
Neutrophil Count	x10  / L		1.5	
Platelet Count	x10  / L		100	550
White Blood Cell Count (WBC)	x10  / L		3	20

Clinical Chemistry				
Laboratory Parameter	Units	Category	Clinical Concern Range	
			Low Flag (< x)	High Flag (>x)
Albumin	g/L		30	
Calcium	mmol/L		2	2.75
Creatinine	umol/L	Δ from BL		↑ 44.2
Glucose	mmol/L		3	9
Phosphorus	mmol/L		0.8	1.6
Potassium	mmol/L		3	5.5
Sodium	mmol/L		130	150

Liver Function				
Test Analyte	Units	Category	Clinical Concern Range	
ALT/SGPT	U/L	High	≥ 2x ULN	
AST/SGOT	U/L	High	≥ 2x ULN	
AlkPhos	U/L	High	≥ 2x ULN	
T Bilirubin	μmol/L	High	≥ 1.5xULN	
T. Bilirubin + ALT	μmol/L U/L	High	1.5xULN T. Bilirubin + ≥ 2x ULN ALT	

### 9.7.2. ECG

ECG Parameter	Units	Clinical Concern Range	
		Lower	Upper
Absolute			
Absolute QTc Interval	msec		> 450 [1]
Absolute PR Interval	msec	< 110 [1]	> 220 [1]
Absolute QRS Interval	msec	< 75 [1]	> 110 [1]
Change from Baseline			
Increase from Baseline QTc	msec		> 60 [1]

**NOTES:**

1. Represent standard ECG values of PCI for HV studies

### 9.7.3. Vital Signs

Vital Sign Parameter (Absolute)	Units	Clinical Concern Range	
		Lower	Upper
Systolic Blood Pressure	mmHg	< 85	> 160
Diastolic Blood Pressure	mmHg	< 45	> 100
Heart Rate	bpm	< 40	> 110

## 9.8. Appendix 8: Abbreviations & Trade Marks

### 9.8.1. Abbreviations

Abbreviation	Description
ADaM	Analysis Data Model
AE	Adverse Event
A&R	Analysis and Reporting
CDISC	Clinical Data Interchange Standards Consortium
CI	Confidence Interval
CV b / CV w	Coefficient of Variation (Between) / Coefficient of Variation (Within)
DBF	Database Freeze
DBR	Database Release
DP	Decimal Places
eCRF	Electronic Case Record Form
EMA	European Medicines Agency
FDA	Food and Drug Administration
FDAAA	Food and Drug Administration Clinical Results Disclosure Requirements
GSK	GlaxoSmithKline
ICH	International Conference on Harmonization
IDSL	Integrated Data Standards Library
ITT	Intent-To-Treat
PCI	Potential Clinical Importance
PDMP	Protocol Deviation Management Plan
PK	Pharmacokinetic
PP	Per Protocol
RAP	Reporting & Analysis Plan
SAC	Statistical Analysis Complete
SDSP	Study Data Standardization Plan
SDTM	Study Data Tabulation Model
TFL	Tables, Figures & Listings

### 9.8.2. Trademarks

Trademarks of the GlaxoSmithKline Group of Companies	Trademarks not owned by the GlaxoSmithKline Group of Companies
NONE	SAS WinNonlin

## 9.9. Appendix 9: List of Data Displays

### 9.9.1. Data Display Numbering

The following numbering will be applied for RAP generated displays:

Section	Tables	Figures
Study Population	1.1 to 1.7	-
Safety	2.1 to 2.21	-
Pharmacokinetic	3.1 to 3.5	3.1 to 3.5
Section	Listings	
ICH Listings	1 to 37	

### 9.9.2. Mock Example Shell Referencing

Non IDSL specifications will be referenced as indicated and if required example mock-up displays provided in [Appendix 10: Example Mock Shells for Data Displays](#).

Section	Figure	Table	Listing
Pharmacokinetic	PK_Fn	PK_Tn	PK_Ln
Safety	SAF_Fn	SAF_Tn	SAF_Ln

**NOTES:**

- Non-Standard displays are indicated in the 'IDSL / Example Shell' or 'Programming Notes' column as '[Non-Standard] + Reference.'

### 9.9.3. Deliverables

Delivery	Description
SAC	Final Statistical Analysis Complete

CONFIDENTIAL

205037

### 9.9.4. Study Population Tables

Study Population Tables					
No.	Population	IDSL / Example Shell	Title	Programming Notes	Deliverable [Priority]
Subject Disposition					
1.1.	Safety	ES1A	Summary of Subject Disposition for the Participant Conclusion Record	ICH E3, FDAAA, EudraCT	SAC
1.2.	Enrolled	ES6	Summary of Screening Status and Reasons for Screen Failure	Journal Requirements	SAC
1.3.	Enrolled	NS1	Summary of Number of Participant by Country and Site ID	EudraCT/Clinical Operations	SAC
Protocol Deviation					
1.4.	Safety	DV1	Summary of Important Protocol Deviations	ICH E3	SAC
Demographic and Baseline Characteristics					
1.5.	Safety	DM3	Summary of Demographic Characteristics	ICH E3, FDAAA, EudraCT	SAC
1.6.	Safety	DM5	Summary of Race and Racial Combinations	ICH E3, FDA, FDAAA, EudraCT	SAC
1.7.	Enrolled	DM11	Summary of Age Ranges	EudraCT	SAC

CONFIDENTIAL

205037

### 9.9.5. Safety Tables

Safety: Tables					
No.	Population	IDSL / Example Shell	Title	Programming Notes	Deliverable [Priority]
Adverse Events (AEs)					
2.1.	Safety	AE1CP	Summary of All Adverse Events by System Organ Class and Preferred Term	ICH E3	SAC
2.2.	Safety	AE5A	Summary of All Adverse Events by Maximum Intensity by System Organ Class and Preferred Term	ICH E3	SAC
2.3.	Safety	AE1CP	Summary All Drug-Related Adverse Events by System Organ Class and Preferred Term	ICH E3 .	SAC
2.4.	Safety	AE5A	Summary of All Drug-Related Adverse Events by System Organ Class and Preferred Term and Maximum Intensity	ICH E3 .	SAC
Laboratory: Chemistry					
2.5.	Safety	LB1	Summary of Chemistry Values		SAC
2.6.	Safety	LB1	Summary of Chemistry Changes from Baseline	ICH E3	SAC
2.7.	Safety	LB4	Summary of Chemistry Data Shifts from Baseline Relative to PCI Criteria	ICH E3	SAC
Laboratory: Hematology					
2.8.	Safety	LB1	Summary of Hematology Values		SAC
2.9.	Safety	LB1	Summary of Hematology Changes from Baseline	ICH E3	SAC
2.10.	Safety	LB4	Summary of Hematology Data Shifts from Baseline Relative to PCI Criteria	ICH E3	SAC

CONFIDENTIAL

205037

Safety: Tables					
No.	Population	IDSL / Example Shell	Title	Programming Notes	Deliverable [Priority]
Laboratory: Urinalysis					
2.11.	Safety	LB1	Summary of Urinalysis Data (Gravity and pH)		SAC
2.12.	Safety	LB1	Summary of Urinalysis Concentration Change from Baseline (Gravity and pH)	ICH E3	SAC
2.13.	Safety	UR3b	Summary of Urinalysis Data (Glucose, Protein, Blood, Ketones, Bilirubin, Urobilinogen)		SAC
Neurological Examination					
2.14.	Safety	NE1	Summary of Neurological Examination		SAC
ECG					
2.15.	Safety	EG1	Summary of ECG Findings	IDSL	SAC
2.16.	Safety	EG2	Summary of ECG Values		SAC
2.17.	Safety	EG2	Summary of Change from Baseline in ECG Values by Visit	IDSL	SAC
2.18.	Safety	HM1	Summary of Cardiac Telemetry	IDSL	SAC
2.19.	Safety	HM2	Summary of Cardiac Telemetry Abnornormalities	IDSL	SAC
Vital Signs					
2.20.	Safety	VS1	Summary of Vital Signs	IDSL	SAC
2.21.	Safety	VS1	Summary of Change from Baseline in Vital Signs	ICH E3	SAC

CONFIDENTIAL

205037

### 9.9.6. Pharmacokinetic Tables

Pharmacokinetic: Tables					
No.	Population	IDSL / Example Shell	Title	Programming Notes	Deliverable [Priority]
3.1.	PK	PK01	Summary of GSK2982772 Plasma Pharmacokinetic Concentration-Time Data		SAC
3.2.	PK	PK03	Summary of Derived GSK2982772 Pharmacokinetic Parameters (non-transformed)		SAC
3.3.	PK	PK05	Summary of GSK2982772 Pharmacokinetic Parameters (log-transformed)		SAC
3.4.	PK	PK_T1	Power Model Analysis for GSK2982772 Dose Proportionality of Pharmacokinetic Parameters (AUC(0-24), AUC(0-7), Cmax)		SAC
3.5.	PK	PK_T2	ANOVA Model Analysis for GSK2982772 Dose Proportionality of Dose-Normalized Derived Pharmacokinetic Parameters(AUC(0-24), AUC(0-7), Cmax)	This table will be provided if the power model fails to converge.	SAC

CONFIDENTIAL

205037

### 9.9.7. Pharmacokinetic Figures

Pharmacokinetic: Figures					
No.	Population	IDSL / Example Shell	Title	Programming Notes	Deliverable [Priority]
3.1.	PK	PK16b	Individual GSK2982772 Plasma Concentration–Time Plots by Subject	A graph on linear and semi-logarithmic scales will be produced.	SAC
3.2.	PK	PK24	Individual GSK2982772 Plasma Concentration–Time Plots by Treatment	A graph on linear and semi-logarithmic scales will be produced.	SAC
3.3.	PK	PK17	Mean (+SD) GSK2982772 Plasma Concentration–Time Plots	A graph on linear and semi-logarithmic scales will be produced. SD will also be displayed.	SAC
3.4.	PK	PK18	Median GSK2982772 Plasma Concentration–Time Plots	A graph on linear and semi-logarithmic scales will be produced.	SAC
3.5.	PK	PK28	Plot of Individual (+Geometric Mean and 95% CIs) GSK2982772 Pharmacokinetic Parameters (AUC(0-24), AUC(0-7), Cmax) versus Dose		SAC

CONFIDENTIAL

205037

### 9.9.8. ICH Listings

ICH: Listings					
No.	Population	IDSL / Example Shell	Title	Programming Notes	Deliverable [Priority]
Subject Disposition					
1.	Screened	ES7	Listing of Reasons for Screen Failure	Journal Guidelines	SAC
2.	Safety	ES3	Listing of Reasons for Study Withdrawal	ICH E3	SAC
3.	Safety	SD3	Listing of Reasons for Study Treatment Discontinuation	ICH E3	SAC
4.	Safety	BL2	Listing of Participants for Whom the Treatment Blind was Broken	ICH E3	SAC
5.	Safety	TA2	Listing of Planned and Actual Treatments	IDSL	SAC
Protocol Deviations					
6.	Safety	DV2	Listing of Important Protocol Deviations	ICH E3	SAC
7.	Safety	IE4	Listing of Participants with Inclusion/Exclusion Criteria Deviations	ICH E3	SAC
Populations Analysed					
8.	Safety	SP3A	Listing of Subjects Excluded from Any Population	ICH E3	SAC
Demographic and Baseline Characteristics					
9.	Safety	DM4	Listing of Demographic Characteristics	ICH E3	SAC
10.	Safety	DM10	Listing of Race	ICH E3	SAC
Prior and Concomitant Medications					
11.	Safety	MH3	Listing of Medical Conditions	IDSL	SAC

## CONFIDENTIAL

205037

ICH: Listings					
No.	Population	IDSL / Example Shell	Title	Programming Notes	Deliverable [Priority]
12.	Safety	CM5	Listing of Concomitant Medications	IDSL	SAC
Exposure and Treatment Compliance					
13.	Safety	EX4	Listing of Exposure Data	ICH E3	SAC
Adverse Events					
14.	Safety	AE9CP	Listing of All Adverse Events	ICH E3	SAC
15.	Safety	AE7	Listing of Subject Numbers for Individual Adverse Events	ICH E3	SAC
16.	Safety	AE2	Listing of Relationship Between Adverse Event System Organ Classes, Preferred Terms, and Verbatim Text	IDSL	SAC
Serious and Other Significant Adverse Events					
17.	Safety	AE9CP	Listing of Fatal Serious Adverse Events	ICH E3	SAC
18.	Safety	AE9CP	Listing of Adverse Events Leading to Withdrawal from Study / Permanent Discontinuation of Study Treatment	ICH E3	SAC
Hepatobiliary (Liver)					
19.	Safety	MH2	Listing of Medical Conditions for Participants with Liver Stopping Events	IDSL	SAC
20.	Safety	SU2	Listing of Substance Use for Participants with Liver Stopping Events	IDSL	SAC
Chemistry					
21.	Safety	LB6	Listing of All Chemistry Data	ICH E3	SAC
22.	Safety	LB6	Listing of All Chemistry Data for Subjects with Any Value of Potential Clinical Importance	ICH E3	SAC
23.	Safety	LB6	Listing of Chemistry Values of Potential Clinical Importance		SAC

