8. DISCONTINUATION CRITERIA

8.1. Discontinuation of Study Treatment

8.1.1. Dose Stopping Criteria

The decision to proceed to the next dose level of GSK2982772 in each part of this study will be made by the principal investigator and GSK Medical Monitor based on safety results (AEs, clinical labs, vital signs, 12-Lead ECGs and findings during continuous cardiac telemetry) obtained in at least 6 subjects having received active treatment (GSK2982772) at the prior dose level.

[figure not shown]
The principal investigator and the GSK Medical Monitor will review the following and dosing will be halted and progression to the next higher dose level stopped if:

- One (1) or more subjects experience a SAE which has a reasonable possibility of relation to study treatment.
- Two (2) or more subjects experience a severe or clinically significant non-serious AE (based upon principal investigator judgment) which has a reasonable possibility of relation to study treatment.
- Two (2) or more subjects experience the same AE of moderate severity which has a reasonable possibility of relation to study treatment.
- Consistent Common Terminology Criteria for Adverse Events (CTCAE) Nervous System AEs of any grade occur across subjects that have a reasonable possibility of relation to study treatment.
- Female partner become pregnant during the treatment period.

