- Medical or surgical procedure (e.g., endoscopy, appendectomy): the condition that leads to the procedure is the AE.
- Situations in which an untoward medical occurrence did not occur (social and/or convenience admission to a hospital).
- Anticipated day-to-day fluctuations of pre-existing disease(s) or condition(s) present or detected at the start of the study that do not worsen.

Definition of SAE

If an event is not an AE per definition above, then it cannot be an SAE even if serious conditions are met (e.g., hospitalization for signs/symptoms of the disease under study, death due to progression of disease).

A SAE is defined as any untoward medical occurrence that, at any dose:

a. Results in death

b. Is life-threatening

The term 'life-threatening' in the definition of 'serious' refers to an event in which the participant was at risk of death at the time of the event. It does not refer to an event, which hypothetically might have caused death, if it were more severe.

c. Requires inpatient hospitalization or prolongation of existing hospitalization

In general, hospitalization signifies that the participant has been detained (usually involving at least an overnight stay) at the hospital or emergency ward for observation and/or treatment that would not have been appropriate in the physician's office or outpatient setting. Complications that occur during hospitalization are AE. If a complication prolongs hospitalization or fulfills any other serious criteria, the event is serious. When in doubt as to whether "hospitalization" occurred or was necessary, the AE should be considered serious.

Hospitalization for elective treatment of a pre-existing condition that did not worsen from baseline is not considered an AE.

d. Results in persistent disability/incapacity

- The term disability means a substantial disruption of a person's ability to conduct normal life functions.
- This definition is not intended to include experiences of relatively minor medical significance such as uncomplicated headache, nausea, vomiting, diarrhea, influenza, and accidental trauma (e.g., sprained ankle) which may interfere with or prevent everyday life functions but do not constitute a substantial disruption.

e. Is a congenital anomaly/birth defect

f. Other situations:

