### 7.1. Adverse Events Analyses

Adverse events analyses including the analysis of adverse events (AEs), Serious (SAEs) and other significant AEs will be based on GSK Core Data Standards. The details of the planned displays are provided in [Appendix 9: List of Data Displays](#).

Display Type	Absolute		
	Summary		Individual
	T	F	L
Adverse Events (AEs)			
All AEs by SOC and PT	Y		Y
All AEs by Maximum Intensity	Y		
Drug-Related AEs by SOC and PT	Y		
Drug-Related AEs by Maximum Intensity	Y		
Subject Numbers for Individual AEs			Y
Relationship Between AE SOCs, PT and Verbatim Text			Y
Serious and Other Significant AEs			
Serious AEs			Y
AEs Leading to Withdrawal from Study			Y

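### SAP 7.1 plans a listing of all serious AEs, but the only SAE-specific listing in Appendix 9 is restricted to fatal events

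*SAP*

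**What the plan says.** SAP 7.1 states its scope broadly: "Adverse events analyses including the analysis of adverse events (AEs), Serious (SAEs) and other significant AEs will be based on GSK Core Data Standards". Its display table has a block headed "Serious and Other Significant AEs" with two rows, one for serious AEs and one for AEs leading to withdrawal. Both are marked for an individual listing and neither for a table. The serious-AE row is not limited by outcome. On the displays themselves, the section says "The details of the planned displays are provided in" Appendix 9.

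In Appendix 9 (SAP 9.9.8, ICH Listings) the corresponding heading also has two entries:

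- Listing 17: "Listing of Fatal Serious Adverse Events"
- Listing 18: "Listing of Adverse Events Leading to Withdrawal from Study / Permanent Discontinuation of Study Treatment"

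Under the preceding adverse-event heading, Listing 14 is the "Listing of All Adverse Events". Listings 14, 17 and 18 all use the shell AE9CP.

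The protocol's SAE definition (Appendix 4, section 12.4) is not confined to death. One criterion, for example, is "Requires inpatient hospitalization or prolongation of existing hospitalization".

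**The concern.** The text of the plan and its display list disagree about a core safety output. Section 7.1 plans a listing of serious AEs whatever their outcome. The entry that should deliver it covers deaths only. A programmer working from the display list would filter on fatal outcome.

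Safety and tolerability is the first objective of this 12-subject study in healthy men. A reader of the study report will look under the serious-AE heading to learn whether any SAE occurred. If Listing 17 is empty because of its filter, that can be mistaken for a finding that there were no SAEs.

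**Working it through.** No statistical calculation applies. The check is a count of the display list and a comparison of the two sections.

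**Step 1. Is a row missing from the list?** SAP 9.9.1 gives the range of ICH listings as 1 to 37. Counting the entries in SAP 9.9.8:

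- Listings 1 to 11: disposition, deviations, populations, demographics, medical conditions
- Listings 12 to 23: concomitant medication, exposure, AEs, liver, chemistry
- Listings 24 to 35: haematology, urinalysis, neurological examination, ECG, vital signs
- Listings 36 to 37: pharmacokinetics

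11 + 12 + 12 + 2 = 37, without a gap. The stated range is reproduced, so a separate listing of non-fatal SAEs has not been lost from the text.

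**Step 2. Match the two sections.**

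| SAP 7.1 row | Appendix 9 entry | Match? |
|---|---|---|
| Serious AEs, listing, any outcome | Listing 17, fatal only | Narrower |
| AEs leading to withdrawal, listing | Listing 18, withdrawal or permanent discontinuation | Broader |

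The rows pair one to one, so Listing 17 is the only counterpart of the planned serious-AE listing.

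**Step 3. Look for any other SAE-specific display.** Of the 37 listings, one is specific to SAEs (Listing 17). None covers non-fatal SAEs or all SAEs. Of the 21 safety tables in SAP 9.9.5, none is restricted to SAEs. Tables 2.1 to 2.4 count AEs by term, intensity and relationship, with SAEs among the rest.

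**Step 4. Follow each kind of SAE through the listings** (Safety population, titles taken literally).

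| SAE | Listing 14 | Listing 17 | Listing 18 |
|---|---|---|---|
| Fatal | Yes | Yes | Depends on action recorded |
| Non-fatal, leads to withdrawal or discontinuation | Yes | No | Yes |
| Non-fatal, leads to neither | Yes | No | No |

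The last row is the gap. Two plain examples fall in it: an SAE judged unrelated, with the subject continuing, and an SAE arising after a subject's last dose when he then completes the study. The second is a foreseeable case in this design. Groups A, B and C receive 240 mg TID in Period 4, their last period, so 3 + 3 + 3 = 9 of the 12 planned exposures to the highest dose are followed only by discharge and the follow-up visit. SAEs are collected until that visit, and no treatment then remains to be discontinued.

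**The case against.** The strongest reply is that nothing is lost and that this is a matter of a title. Much of that stands. Listing 14 holds every AE, and with 12 planned subjects it should be short. Listing 18 sits under the same heading as Listing 17. Under Protocol 8.1.4, a serious AE judged related meets the individual stopping criteria, so a related non-fatal SAE occurring while dosing continues would be expected in Listing 18, with the reason in Listing 2 or 3. It is also true that no sentence says Appendix 9 overrides Section 7.1, so the fatal-only filter might not be applied in practice.

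This does not remove the mismatch. Listing 18 is not an SAE listing and misses the cases in the last row of step 4. Listing 14 mixes serious and non-serious events, and since shell AE9CP is not reproduced, the documents do not show whether SAEs can be picked out there. If it is unclear which of the two sections governs, that is itself a reason to align them.

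Some stronger readings are tempting but not supported:

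- *The serious-AE section of the report would be empty, or non-fatal SAEs could be found only in the all-AE listing.* Listing 18 contradicts both.
- *An SAE summary table is missing.* Section 7.1 marks serious AEs for a listing only, and Appendix 9 agrees.
- *Earlier experience shows that an SAE here would most likely be non-fatal.* Protocol 3.2 reports neither deaths nor non-fatal SAEs in the first-in-human study, so it does not bear on the split.
- *The halting rule is weakened.* Protocol 8.1.1 halts dosing if "One (1) or more subjects experience a SAE which has a reasonable possibility of relation to study treatment". The principal investigator and Medical Monitor apply that rule during the study, and SAEs are reported to the sponsor within 24 hours (Protocol 9.1.1). Listing 17 is produced only after study completion and database freeze (SAP 3.2).

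**Conclusion.** The inconsistency is real and should be corrected. As titled, the one SAE-specific display in the plan omits all non-fatal SAEs, contrary to Section 7.1. The practical gap is narrower: a non-fatal SAE leading to neither withdrawal nor discontinuation would appear in neither listing under the serious and significant heading, and would be visible only among all AEs in Listing 14 and, for a drug-related or any other AE, in the pooled counts of Tables 2.1 to 2.4.

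This rests on two assumptions: that the listings are programmed to their titles, and that AE9CP cannot be relied on to flag seriousness. If the shell does carry a seriousness flag, SAEs could be identified in Listing 14 and the matter is mainly one of consistency. Data collection, analysis populations, estimates and error rates are unaffected.

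**What to change.** Retitle Listing 17 as *Listing of Serious Adverse Events (Fatal and Non-Fatal)* and change its filter from fatal SAEs to all SAEs. Appendix 9 then matches Section 7.1, the shell stays AE9CP, and the list stays at 37. The cost is one title and one filter condition.

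Alternatively, keep Listing 17 and add a listing of non-fatal SAEs after it. That makes 37 + 1 = 38 listings, so the later ones must be renumbered and the range in SAP 9.9.1 updated. The first option is simpler. Neither needs new data or a protocol change.

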## CONFIDENTIAL

205037

ICH: Listings					
No.	Population	IDSL / Example Shell	Title	Programming Notes	Deliverable [Priority]
Haematology					
24.	Safety	LB6	Listing of All Haematology Data	ICH E3	SAC
25.	Safety	LB6	Listing of All Haematology Data for Subjects with Any Value of Potential Clinical Importance	ICH E3	SAC
26.	Safety	LB6	Listing of Haematology Values of Potential Clinical Importance		SAC
Urinarysis					
27.	Safety	LB6	Listing of Urinarysis Data (Gravity and pH)		SAC
28.	Safety	LB14	Listing of Urinarysis Data (Glucose, Protein, Blood, Ketones, Bilirubin, and Urobilinogen)		SAC
Neurological Examination					
29.	Safety	NE2	Listing of Neurological Examinations	IDSL	SAC
ECG					
30.	Safety	EG6	Listing of ECG Findings		SAC
31.	Safety	EG4	Listing of All ECG Values	IDSL	SAC
32.	Safety	EG4	Listing of All ECG Values for Subjects with Any Value of Potential Clinical Importance	IDSL	SAC
33.	Safety	HM10	Listing of Clinically Significant Cardiac Telemetry Abnormalities	IDSL	SAC
Vital Signs					
34.	Safety	VS5	Listing of All Vital Signs Data	IDSL	SAC
35.	Safety	VS5	Listing of All Vital Signs Data for Subjects with Any Value of Potential Clinical Importance	IDSL	SAC

## CONFIDENTIAL

205037

ICH: Listings					
No.	Population	IDSL / Example Shell	Title	Programming Notes	Deliverable [Priority]
Pharmacokinetics					
36.	PK	PK08	Listing of GSK2982772 Plasma Pharmacokinetic Concentration-Time Data	IDSL	SAC
37.	PK	PK14	Listing of Derived GSK2982772 Plasma Pharmacokinetic Parameters	IDSL All PK parameters in Section 8.1.1.2 will be provided in a listing	SAC

CONFIDENTIAL

205037

